Introduction. Older adults have reduced adaptive and regenerative capacities to recovery from a surgical insult.²⁷ Thus, when coupled with insufficient energy intake, malnutrition becomes the driver that leads to further deterioration of functional abilities, reduction in lean muscle mass, and inability to maintain physical reserve. A generous and balanced intake of high quality protein (~30 grams) is essential for achieving optimal protein synthesis in older adults²⁸ and is linked to lean mass retention.²⁹ The essential amino acids

found in complete (animal) proteins stimulate translation initiation of the mTOR signaling pathway and increase muscle protein synthesis in older individuals.²⁹ The objective of this aim is to research the effects of a meal-based protein enhanced perihabilitation intervention in malnourished older Veterans undergoing elective surgery on the primary outcome physical function and secondary outcomes, inflammatory biomarkers (albumin, hsCRP, TNF- α , IL-6), dietary intake, hospital readmission, discharge location, length of skilled care, and ED admission, and physical activity. To achieve the objective of this aim, we will test the working hypothesis that Veterans consuming the enhanced protein supplementation will have superior improvements in function compared to the control arm. Approach: We will further refine our working hypothesis in a two-armed pilot trial comparing a high protein nutrition supplement for two weeks pre and post-surgery to an education control arm. We will assess physical function (SPPB) and secondary outcomes two weeks before, the day of surgery, and four weeks post-surgery. The successful completion of the proposed research will provide preliminary data to test this hypothesis in a large scale randomized controlled trial. When the proposed studies for Aim 1.2 have been completed, it is our expectation that the protein intervention will prove to provide higher functional and physiological benefits relative to the control treatment, illustrating the importance of nutritional perihabilitation prior and following surgery in high-risk, vulnerable populations.

Design

[figure not shown]
This is a Randomized Controlled Study. Veterans will be enrolled until 84 participants have completed the study.

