Setting: The POSH Clinic is an interdisciplinary collaboration between surgery, anesthesiology, geriatrics, nursing, and physical therapy to provide perioperative surgical care for high-risk Veterans at the Durham VAMC. The clinic opens with a conference to review patients to be seen that day. The surgery chief resident presents and the team covers technical issues with the surgery and selection of anesthesia, as well as covering a list of specific care points. The POSH clinic estimates 200 – 400 patients enrolled annually.

VAPOSH Veterans who are malnourished or at risk of being malnourished will be randomly assigned on a 1:1 ratio by computer-generated random numbers to either an education (nutritional counseling) control (PoshControl) arm or high-protein perihabilitation (PeriHab) arm. All will receive nutrition education. Participants in the PeriHab arm will also be provided with high quality protein supplements that will bring their protein intakes to at least 30 grams for each of the 3 meals per day.

Study Arms:

- PoshControl; n = 42: During their VAPOSH clinic visit, participants will be provided nutrition counseling and prescribed to consume protein at 1.0 g/kg of body weight in the form of educational handouts explained by a Registered Dietitian. Participants will also be instructed to consume 1 oral nutrition supplement per day two weeks before surgery.
- PeriHab; n = 42: PeriHab will be provided nutrition counseling and prescribed to consume protein at 1.6 g/kg of body weight) as well as provided 30 g of high quality protein to some 3 times per day for 2 weeks before and 4 weeks after surgery.

Measurements:

After the participant has been consented and HIPAA Authorization forms have been signed, a Registered Dietitian will administer the NRS-2002 screening tool, the PG-SGA, and nutrition focused physical exam. A patient screening “nourished” on the NRS-2002, PG-SGA, and nutrition focused physical exam will not be included in the study. For study candidates who are malnourished or at nutritional risk we will then proceed with baseline assessments (described below). Upon the completion of all baseline assessments, the participant will be randomized to PeriHab or PoshControl. The following variables will be blocked in this order: 1) surgery type and 2) American Society of Anesthesiology (ASA) Physical Status Classification System (≥ 3 versus < 3). An equal number of participants will be randomized across the two arms.

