Measures and Data Collection Points

| Measure | When Collected |
|------------------------------------|-----------------------|
| NSR-2002 | Baseline (T1), T2, T3 |
| PG-SGA | T1, T2, T3 |
| Nutrition Focused Physical Exam | T1, T2, T3 |
| Cognition | T1 |
| Medical History | T1 |
| Demographic | T1 |
| Anthropometrics | T1, T2, T3 |
| Comorbidity Status | T1 |
| Bristol Stool Chart | T1 |
| Short Physical Performance Battery | T1, T2, T3 |
| Handgrip strength | T1, T2, T3 |
| Biological Markers | T1, T2, T3 |
| Postoperative outcomes | T3 |

| | |
|---|----------------------------|
| Physical Activity | T1, T2, T3 |
| PROMIS and PROMIS GLOBAL QUESTIONNAIRES | T1, T2, T3 |
| Three-day Food Record | T1, T2, T3 |
| Protein Checklist | Daily |
| 24-Hour Dietary Recall | Weekly between time points |
| Participant Satisfaction Questionnaire | T3 |
| Participant Acceptability | T3 |

Risk/Benefit Assessment

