The PI will meet at least weekly with study personnel to discuss participants' reactions to outcome measures and assessments, weekly telephone calls, and any adverse events or unanticipated problems. Monthly meetings between the investigators and the project coordinator will allow for ongoing progress reports, including the number of participants currently involved in the study and scheduled data collection from participants, as well as notification and review of any AEs. Safety monitoring for adverse events (AEs) will be conducted in real time by the PI and/or project coordinator. The following information about adverse events will be collected: 1) the onset and resolution of the AE, 2) an assessment of the severity or intensity (use existing grading scales whenever possible), 3) an assessment of the relationship of the event to the study (definitely, probably, possibly or not related), and 4) action taken (e.g., none, referral to physician, start or increase concomitant medication). The PI will determine the severity of the event, will assign attribution to the event, and will monitor the event until its resolution. All adverse events will be reported per Durham VAMC requirements. All Serious, Unanticipated and Related adverse events will be reported to IRB within 5 business days of hearing of the event. All other adverse events will be reported at continuing review.

Withdrawal of Participants

Subjects who do not have surgery will be withdrawn from the study. Additionally, if a subject has to have emergency surgery, rather than elective surgery during the two weeks between the POSH clinic visit and their scheduled surgery date they will be withdrawn from the study. Finally, subjects who refuse to consume protein supplement will be withdrawn from the study.

If a participant decides to withdraw from the study, they will be instructed to contact the PI and discuss the reason for withdraw. This information will be documented to help better understand the reasons that the participant was unable to complete the study.

Data Analysis and Statistical Considerations

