Aim 1.2 Analysis Plan: This design is a two-armed clinical trial, with replicate measures at three time points: baseline, two, and six weeks. Since subjects are randomized to either PeriHab or PoshControl arm, and the groups are presumed equal at baseline, the analysis is straightforward. Following the Good Clinical Practice Guidelines for the analysis of a clinical trial, we will employ mixed models,⁴³ analyze under an Intent to Treat (ITT) criteria, and control for baseline and assess the impact of Time, Treatment Group and the interaction of these variables on the outcomes. Relative to the usual repeated measures designs, mixed models have several advantages: 1) missing values present no particular difficulties in estimation and the estimates are unbiased as long as the set of variables leading to MAR are estimated, 2) the usual assumption of conditional independence (compound symmetry) used in standard repeated measures need not be made, and 3) the actual times of measurement need not be equivalent across subjects. Controlling for the individual baseline values for the particular outcomes, the trajectories over time and differences in those trajectories will be assessed. Following the statistical principles section from the International Conference on Harmonization, we will select covariates (e.g., age, race, number of comorbidities) for the primary models a priori, but we also will conduct auxiliary sensitivity analyses that evaluate whether potential group imbalances bias the treatment effect estimate. These analyses will be performed using conventional testing for confounding.

For any particular outcome, the general form of the model will be:

$$Y_{it} = \beta_0 + \beta_1(\text{group}) + \beta_2(\text{time}_t) + \beta_3(\text{group} * \text{time}_t) + \beta_4(\text{covariates}) + \varepsilon_{it}$$

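### Withdrawals after randomisation turn the declared intent-to-treat comparison of function into a comparison of participants who reached elective surgery

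*Combined protocol and SAP*

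**What the plan says.** **Order of events.** Under Measurements, "Upon the completion of all baseline assessments, the participant will be randomized to PeriHab or PoshControl". This happens around the clinic visit. The chart review under Subject Recruitment requires a surgery date at least two weeks after that visit, so every participant waits at least two weeks between clinic visit and operation.

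**Withdrawal.** The Withdrawal of Participants section has three rules. The first is "Subjects who do not have surgery will be withdrawn from the study". The second applies "if a subject has to have emergency surgery, rather than elective surgery during the two weeks between the POSH clinic visit and their scheduled surgery". The third is "Finally, subjects who refuse to consume protein supplement will be withdrawn from the study". Each ends participation in the study, not just use of the supplement.

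**Outcome.** Physical function (SPPB) is the primary outcome of Aim 1.2. The approach text places assessments "two weeks before, the day of surgery, and four weeks post-surgery", and the measures table lists "Short Physical Performance Battery | T1, T2, T3".

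**Analysis.** The Aim 1.2 Analysis Plan uses mixed models and says the team will "analyze under an Intent to Treat (ITT) criteria, and control for baseline". The model has two outcome times only, labelled weeks 2 and 6.

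**Numbers.** The Design section continues enrolment until 84 have completed. The feasibility analysis plan (headed Aim 2.1) divides those retained by all randomised, sets a target of at least 80%, and reports retention by group.

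The documents do not define the ITT set. They provide no follow-up after withdrawal, no substitute assessment date when the planned operation does not happen, and no sensitivity analysis for these withdrawals.

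**The concern.** All three rules act after randomisation and, in most cases, after the intervention has begun. Whether a malnourished older patient reaches the planned operation may depend on how that patient fares in the waiting period, which is when the arms are treated differently. Restricting the comparison to those who reach elective surgery is then selection on a post-randomisation event, and the ITT label hides it.

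The third rule departs from ITT most directly because it depends on adherence. The burden also differs by arm: three supplements a day before and after surgery in PeriHab, against one a day before surgery in PoshControl.

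What is at stake is the product of Aim 1.2, an effect size for planning a larger trial. If that trial is sized for everyone randomised, an estimate from those who reached elective surgery answers a different question.

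**Working it through.** **1. The plan's own figure.** With 40 per group, two-sided alpha 0.05 and 80% power, a two-sample t calculation gives a detectable difference of 0.6343 SD. The Power Estimate states 0.634, so it reproduces. The normal approximation, (1.960 + 0.842) × √(2/40), gives 0.626. The sample-size arithmetic is not in dispute here.

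**2. What each withdrawn participant contributes to the model.**

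| Path | T1 SPPB | T2 (day of surgery) | T3 (four weeks after) | Outcome rows |
|---|---|---|---|---|
| No operation | yes | does not occur | does not occur | 0 |
| Emergency operation before the planned date | yes | withdrawn | obtainable, but withdrawn | 0 |
| Refuses supplement before T2 | yes | obtainable, but withdrawn | obtainable, but withdrawn | 0 |
| Refuses supplement after T2 | yes | yes | obtainable, but withdrawn | 1 |

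T1 SPPB exists for everyone randomised, but baseline enters the model as a covariate. A participant with T1 alone adds nothing to the group or group-by-time terms.

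**3. How many could be absent.** Randomised = 84 / (1 − w), rounded up, where w is the proportion lost. The documents give no rate of cancellation, emergency surgery or refusal. The only bound is the 80% retention target, which covers loss from every cause.

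- w = 5%: 84/0.95 = 88.4, so 89 randomised and 5 absent
- w = 10%: 84/0.90 = 93.3, so 94 randomised and 10 absent
- w = 15%: 84/0.85 = 98.8, so 99 randomised and 15 absent
- w = 20%: 84/0.80 = 105 randomised and 21 absent

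**4. Possible bias.** Let p be the proportion of an arm lost by these paths, and D how far below the remaining participants their mean SPPB would have been, in SD of SPPB. The mean of all randomised in the arm is c − pD, where c is the mean of those who stay, so the arm mean is raised by pD. With the same D in both arms, the bias in PeriHab minus PoshControl is (p_PeriHab − p_PoshControl) × D.

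Assumed: differences between arms of 5 or 10 points, and D of 0.5 or 1.0.

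- 5 points: 0.05 × 0.5 = 0.025; 0.05 × 1.0 = 0.05
- 10 points: 0.10 × 0.5 = 0.05; 0.10 × 1.0 = 0.10
- Equal proportions and equal D: 0

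With D positive, the effect is overstated if PeriHab loses more and understated if PoshControl loses more. If D is negative, both signs reverse. D here is not adjusted for baseline; only the part not explained by baseline SPPB and the model's covariates would bias the estimate.

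**5. Against sampling error.** With 42 per arm, the standard error of a standardised difference is about √(2/42) = 0.218, and the 95% half-width is 1.96 × 0.218 = 0.43. The bias range is 0.025/0.218 = 0.11 to 0.10/0.218 = 0.46 of a standard error.

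**The case against.** The strongest reply is that this is a pilot. Even the top of the bias range is under half a standard error, and it needs a 10-point difference between arms together with a full SD deficit. Controls also receive counselling and a daily supplement before surgery, and nothing in the documents points to so large a difference. That stands as a limit on size. It does not make the analysis ITT.

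The assumed deficit is also doubtful for participants who have no operation. They avoid the surgical insult that the Aim 1.2 introduction links to functional decline, and may score better than operated patients. The plan gives no reason for a missed operation; it could be scheduling or patient choice. This stands, and it leaves the direction of bias open.

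The plan notes that mixed models tolerate missing values. It makes this conditional on the variables that drive missingness being in the model. Its example covariates (age, race, number of comorbidities) do not capture a cancellation or an emergency after randomisation. The week 2 and week 6 labels do not help either, since no text provides a calendar visit for someone withdrawn.

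Retention over all randomised, compared by arm, would show unequal loss. It does not put the lost participants back into the function comparison.

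Finally, Aim 1.2 is framed around older Veterans having elective surgery, so a declared modified-ITT set could be defended. That is fair, but the plan declares ITT instead.

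**Conclusion.** The point holds as a mismatch between the withdrawal rules and the declared analysis. As written, the ITT comparison of SPPB is a comparison of participants who reached elective surgery and were not withdrawn for refusing supplement. That follows from the text and needs no assumed rate.

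The numerical effect cannot be determined from the documents. It is nil if losses and outcomes are balanced, and about 0.025 to 0.10 SD of SPPB under the assumptions above, with the direction unknown. The figure of 21 absent out of 105 is what the retention target tolerates from all causes, not a forecast of these events.

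Three stronger readings are not supported:

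- A reader might infer that withdrawals leave the trial short of completers. The Design section enrols until 84 complete, so losses are replaced. Selection of Subjects, which screens and consents up to 84, is less clear but does not establish a shortfall.
- A reader might infer that withdrawn participants have no SPPB at all. T1 SPPB is taken before randomisation; only post-baseline scores are missing.
- A reader might express the bias as a share of 0.634. That figure rests on SDs of change in the 6-minute walk, so it is not a yardstick for SDs of SPPB.

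**What to change.** Reconcile Withdrawal of Participants with the Aim 1.2 Analysis Plan by separating withdrawal from the intervention from withdrawal from follow-up.

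- **Emergency surgery:** keep the participant in the ITT set, assess SPPB four weeks after the actual operation, and take post-operative outcomes (readmission, discharge location, skilled care, ED use) from VA records. The data management section already foresees downloads of VA patient information, and the analysis plan accepts unequal measurement times.
- **No operation:** choose one rule and state it. Either obtain SPPB at about weeks 2 and 6 from T1 where feasible, or openly declare a modified-ITT set of those who had surgery. The first option pools unoperated with post-operative function, and its dates need not match other participants' T2 and T3. The second still conditions on a post-randomisation event and must be labelled so.
- **Reporting:** define the ITT set, report all three kinds of withdrawal by arm and reason, and give the elective-surgery-only analysis as a sensitivity analysis.

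The cost is protocol wording, a check that consent covers continued follow-up and record use, and a few extra visits. The estimate may also be slightly smaller. If 5% or 10% of those analysed were retained with no treatment effect (an assumption), the plan's 0.634 would become 0.634 × 0.95 = 0.602 or 0.634 × 0.90 = 0.571. Power with 42 per arm would fall from 81.9% to 77.9% or 73.4%. These figures inherit the plan's walk-test basis and only illustrate the dilution.

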Introduction. Malnutrition is recognized as a major concern by healthcare providers, as well as by patients, families, and caregivers. In a very recent survey, 28% of 1,035 patients, families and caregivers reported that malnutrition was a very significant problem, while 55% reported it was a somewhat significant problem in older adults 65 and older.²⁶ This response aligns with reports that up to 65% of older adults admitted to the hospital are malnourished (National Resource Center on Nutrition, Physical Activity, and Aging, 2015). Thus, it is essential to establish systematic malnutrition screening in the clinical setting and to develop intervention models and standards of nutritional care. The objective of this aim is to investigate the feasibility, fidelity and acceptability of a nutrition intervention protocol providing higher protein intakes before and after surgery in malnourished Veterans. To achieve the objective of this aim, we will test our working hypotheses that recruitment in clinic will have a high yield and that intervention fidelity (adherence, retention) and acceptability (attrition, patient satisfaction) will be predominantly satisfactory. The rationale for this aim is that successful completion of the proposed research will provide necessary knowledge to begin to identify feasible and acceptable interventions for community-dwelling Veterans who are preparing for surgical procedures. When the proposed studies for Aim 1.1 have been completed, it is our expectation that $\geq 75\%$ of patients approached for recruitment will agree to participate, $\geq 75\%$ of the time patients will adhere to the intervention, $\geq 80\%$ of the participants will remain in the study, and that $\geq 80\%$ of participants will find the intervention to be acceptable. Such findings would be of considerable importance, providing a patient-centered viewpoint that will inform the development of nutrition interventions that meet the standards and needs of high-risk Veteran Populations.

Specific Aim 1.2 – *To determine the effect size for planned future studies of enhanced protein supplementation in malnourished Veterans, with physical function as the primary outcome of interest. Of secondary interest are: biomarkers of inflammation (albumin, hsCRP, TNF- α , IL-6), dietary intake, hospital readmission, discharge location, length of skilled care, and ED admission, and physical activity.*

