Where i is an indicator of person, and time is defined as $t=1, 2$ (measuring week 2 or 6), and the β 's are regression coefficients connecting the predictors to the outcome. For brevity, we list β_4 as a vector of K regression coefficients linking the K covariates to the outcome. As defined, the overall test of the intervention effect will be the joint effect of group and group*time on 2 df (β_1 and β_2) assessing an overall effect of group, and if this group effect is constant over time. If significant, follow-up tests will assess where group differences lie. In particular, we note that if the time by group interaction is rejected, we will test if the groups differ at the end of 6 weeks (a test of effect at the completion of the intervention).

We will carefully examine model assumptions, including the distribution of model residuals, additively, linearity, and influential observations, and will, if necessary, re-parameterize the models or transform the outcomes accordingly.

We note that we have listed numerous measures to be analyzed as outcomes, but have listed only 2 domains of outcomes as primary (physical function and a biological index of nutrition status and inflammation). We will not adjust for Type-I error rate for these primary outcomes. Rather, we will warn the reader of the multiple outcomes tested and the chance for a Type-I error.

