The results of these analyses will provide invaluable information regarding the process and functional forms and, potentially, the causal pathways of the intervention process. For example, one important analysis will enter 'level of compliance to the intervention' into the analysis, allowing for a 'per protocol' analysis of the results.

Power Estimate: Estimate effect sizes for the physical function between-group comparisons and the power available to detect effect with two-tailed tests are provided below for the total N= 80. The objective of this pilot study is to perform preliminary evaluation of a nutrition perihabilitation program in malnourished Veterans, in preparation for a larger grant submission. This pilot work will allow us to conduct sample size, effect sizes, and power analyses for a larger clinical trial. To date, no randomized controlled nutrition perihabilitation study has been conducted in malnourished Veterans. As such, we turned to the literature. Gillis et al.,⁴⁶ reported that older adults undergoing colorectal resectioning surgery who were given nutrition supplementation 3 weeks before surgery improved by 23.7 meters on the 6 minute walk test while the arm given nutrition supplement following the surgery declined by -21.3 meters. The pooled standard deviation of these changes was 67.75. Thus, a standard difference of $0.66 = (23.7 - (-21.3))/67.75$ was observed. Differences of this magnitude have been labeled as 'medium' in the statistical power literature (70). Assuming a standard deviation in the change scores of 67.75, n=40 per group, power=80% and alpha=0.05 (two-tailed), we are powered to detect a difference in changes scores of a standardized magnitude of 0.634, in line with the results of Gillis et al.⁴⁶

References

2. Morley J. Decreased food intake with aging. *J Gerontol Med Sci* 2001;56:81-88.

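### Participants who refuse the supplement after randomization leave the study with no planned T2/T3 assessment, so outcomes the ITT analysis needs are lost, and their place in the adherence denominator is undefined

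*Combined protocol and SAP*

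**What the plan says.** Under Withdrawal of Participants, "subjects who refuse to consume protein supplement will be withdrawn from the study". The wording covers the study, not only the supplement. The one further provision there is for participants who themselves decide to withdraw: they speak to the principal investigator and the reason is recorded. No section mentions T2 or T3 assessment after withdrawal.

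On timing, the Measurements section says: "Upon the completion of all baseline assessments, the participant will be randomized to PeriHab or PoshControl". Study Interventions has the PeriHab supplement handed out at the T1 clinic visit, three per day before and after surgery. Controls are asked to take one supplement per day before surgery only.

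The Aim 1.2 Analysis Plan promises to "analyze under an Intent to Treat (ITT) criteria" with a mixed model. Baseline is controlled for, and the modelled times are weeks two and six ("measuring week 2 or 6"). On missing values it says "the estimates are unbiased as long as the set of variables leading to MAR are estimated". The Secondary Outcomes text adds an analysis using "level of compliance to the intervention".

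The feasibility analysis (headed Aim 2.1 Analysis Plan) divides empty supplement containers by the containers that could have been consumed, and does not mention withdrawn participants. Retention, by contrast, is explicitly over all randomized, and is reported and tested by group. The stated purpose of Aim 1.2 is "To determine the effect size for planned future studies".

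**The concern.** The withdrawal rule ends follow-up because a participant declined the assigned treatment. An ITT comparison needs outcomes from everyone randomized, whether or not they took it. If refusers differ from those who stay, in ways the covariates do not capture, the week-6 comparison no longer describes the randomized groups.

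The rule may also bite unequally. PeriHab participants face three supplements a day before and after surgery; controls face one a day before surgery. The text does not say whether the rule reaches the control supplement at all.

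Two pilot results are exposed. The first is the effect size passed to the larger trial: if it is too large, that trial is sized too small. The second is container adherence, whose value depends on an unstated choice about refusers. Satisfaction is affected too, because the questionnaire is given only at T3.

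**Working it through.** **1. The plan's own figure.** Inputs from Power Estimate: 40 per group, 80% power, two-sided alpha 0.05. A two-sample t calculation gives a detectable standardized difference of 0.634, matching "we are powered to detect a difference in changes scores of a standardized magnitude of 0.634". Nothing below disputes that figure.

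**2. What a refuser contributes.** The modelled outcomes are weeks 2 and 6, with baseline as a covariate.
- Withdrawn before T2: no outcome record.
- Withdrawn after T2: week 2 only.

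Under MAR the model can use the week-2 value in the second case. In the first it has only covariates to go on.

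**3. Size of a possible bias (illustration).** The documents give neither a refusal rate nor an outcome gap, so both are assumed. Let k of 42 PeriHab participants refuse, and let the gap be how much worse they do, in SD units, after covariate adjustment. The overstatement of the PeriHab mean is k/42 × gap.
- k = 4, gap 0.5: 4/42 × 0.5 = 0.048 SD.
- k = 8, gap 1.0: 8/42 × 1.0 = 0.190 SD.
- If enrolment continues until 42 PeriHab participants complete (the Design section enrols to 84 completers), 8 refusers make 50 randomized: 8/50 × 1.0 = 0.16 SD.

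A simulation of the week 2/6 model (4,000 runs, 42 per arm, assumed residual correlation 0.6) gave these week-6 biases:

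| Refusers leave | 4 refusers, gap 0.5 | 8 refusers, gap 1.0 |
|---|---|---|
| Before T2 | 0.05 | 0.19 |
| After T2, gap only at week 6 | 0.05 | 0.19 |
| After T2, gap already present at week 2 | 0.02 | 0.08 |

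For scale, the standard error of the difference with 42 v 34 is √(1/42 + 1/34) = 0.23 SD.

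**4. Consequence for a later trial, same assumptions.** If the pilot reported 0.634, the all-randomized effect would be 0.634 − 0.048 = 0.586 or 0.634 − 0.190 = 0.444. At 80% power these need 47 or 81 per arm, against 41 for 0.634.

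**5. Container adherence.** Assume the other PeriHab participants use 80% of their containers and refusers use none.
- Refusers left out: 80%, whatever their number.
- Refusers counted, 2 of 42: 40/42 × 0.80 = 76.2%.
- Refusers counted, 3 of 42: 39/42 × 0.80 = 74.3%.

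Three refusers are enough for the choice to decide whether the 75% hypothesis is met.

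**6. Retention.** With 8 PeriHab refusers and no other loss, retention is 34/42 = 81.0% in that arm and 76/84 = 90.5% overall, both above the 80% hypothesis. The planned by-group test on 34/42 v 42/42 gives chi-square 8.84, p = 0.003.

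**7. Satisfaction.** If 61 of 76 responders are satisfied (80.3%) and 8 are unassessed, the figure for all 84 lies between 61/84 = 72.6% and 69/84 = 82.1%.

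**The case against.** The strongest reply is that the rule does not contradict ITT. No section deletes data already collected or removes withdrawn participants from the analysis set, so they can be analysed as randomized under MAR. This stands as a limit. A reader might infer that refusers are formally excluded from the analysis; the documents do not say so. What remains is avoidable missing outcomes, caused by a rule tied to accepting treatment. The planned sensitivity analyses, on group imbalance and on predictors of adherence, do not address data not missing at random.

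A reader might also infer that every poor adherer is removed, so that the compliance analysis collapses onto the main one. The documents do not support that. Participants having difficulty are counselled, and only refusal triggers withdrawal. The compliance analysis keeps a range of adherence but loses later outcomes at its lowest end.

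A third inference is that retention would hide the problem. It would not: a large imbalance would show in the by-group test. Attrition is also an acceptability measure, so refusal does count against the intervention. Neither restores the missing outcomes.

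Finally, the direction is assumed. Control refusals, if the rule covers them, would offset the shift, and refusers might do no worse than others. The illustrated bias is below the pilot's standard error, though a systematic error does not average out. The 75% and 80% targets are hypotheses with no stated go/no-go rule.

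**Conclusion.** The concern holds in this form: the plan stops outcome collection in participants who refuse the supplement after randomization, provides no later assessment, and yet promises an ITT analysis of later outcomes. It also leaves refusers' containers undefined in the adherence proportion. Both points rest on the text alone, and confidence in them is high.

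Confidence in any size is low. The range of about 0.05 to 0.19 SD depends on assumed refusal numbers and gaps, on all refusers being in PeriHab, and on their doing worse. It does not establish that the pilot's effect will be inflated. Loss of precision is minor: the detectable difference moves from 0.619 (42 v 42) to 0.655 (42 v 34). The adherence swing from 80% to 74.3% assumes 80% use in the rest and zero use in three refusers.

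This should be fixed, because assessments never made cannot be recovered at analysis. It does not invalidate the pilot.

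**What to change.** - **Follow-up.** Separate refusing the supplement from leaving the study. Seek the scheduled T2/T3 assessments, including the satisfaction questionnaire, from refusers who still consent.
- **Analysis.** State that all randomized participants are analysed as assigned. Add one sensitivity analysis for data not missing at random, for example shifting missing week-6 values over a range in either arm. Reconcile Withdrawal of Participants with the Aim 1.2 Analysis Plan.
- **Adherence.** Define the primary container proportion over all randomized PeriHab participants. Count as possible the containers scheduled during the participant's supplement period, with refused containers counted as not consumed. Do not count supply never issued because surgery did not take place. Report retained participants only as a secondary figure.
- **Reporting and scope.** Give satisfaction non-responders by arm beside the percentage. State whether the withdrawal rule covers the control supplement.

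No change to who receives supplement is proposed.

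The cost is protocol and SAP wording, one extra analysis, staff time, and payments of at most $40 (T2) + $80 (T3) = $120 per refuser, or $960 for eight. Adherence and effect-size figures may come out less favourable, and some refusers will decline follow-up.
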